IBC	Institutional Biosafety Committee
ICD	Informed Consent Document
ICH	International Conference of Harmonization
IDE	Investigational Device Exemption
IDS	Investigational Drug Service
IND	Investigational New Drug
IRB	Institutional Review Board
LAR	Legally Authorized Representative
OHRP	Office of Human Research Protections
OPRS	Office for the Protection of Research Subjects
PHI	Protected Health Information
PI	Principal Investigator
PPRA	Protection of Pupil Rights Amendment
QA/QI	Quality Assurance/Quality Improvement
SAE	Serious Adverse Event
SOP	Standard Operating Procedure

1.0 Project Summary/Abstract

Chronic kidney disease (CKD), affects over 45% of all individuals over 70 years of age. Patients with moderate CKD have more than a two-fold increased risk of cognitive impairment than those without CKD; furthermore, as many as 20-70% of patients with CKD have established cognitive impairment and overt dementia. The burden of cognitive impairment and dementia leads to functional decline and accelerated loss of independence, contributing to the tremendous individual, societal, and economic burden of CKD (i.e., 20% of Medicare expenditures in adults >65 years of age). There is no recommended treatment to prevent cognitive decline in CKD patients, and the few medications available for cognitive impairment have only short term modest effects. There is a critical need to evaluate therapies to forestall cognitive impairment, and maintain or improve cognitive functioning in older patients with CKD. To address this need, we will test the hypothesis that older patients with moderate/severe CKD and pre-clinical cognitive impairment randomized to a 6-month home-based exercise program will improve cognitive function and MRI measured brain structure, compared to a usual care control group. We are focusing on patients with pre-clinical cognitive impairment in order to capture a therapeutic window in the disease process, which will allow us to possibly prevent dementia before brain atrophy becomes irreversible. **This is a pilot study for feasibility.** Our central hypothesis is that the accelerated cognitive decline in CKD results from a vascular dysfunction-induced reduction in the integrity of the brain white matter and that exercise training provides a cerebro-protective effect by improving cerebral vascular health. We will combine an assessment of cognition with MR imaging techniques to fully evaluate brain structure, blood flow, and behavior relationships at a level previously not conducted in this population. This study is designed to improve or forestall cognitive decline in CKD patients by establishing an intervention that is implemented individually in the community, and will provide the first step in providing an effective treatment designed to delay physical and cognitive function-related loss of independence, and curb the escalating costs in the growing CKD population. This is a population with accelerated brain aging and a high prevalence of cognitive impairment, making the potential clinical impact tremendous.

Anticipated risks associate with the study: We will monitor heart rate and blood pressure during all testing. There is a very small risk associated with the 6 minute walk exercise test and training. The risk of serious adverse events (such as death or heart attack) with maximal exercise testing has been estimated to be 0.5 per 10,000 tests (Stuart, 1980 Chest), the risk of death associated with a 6-minute walk is currently not known, but is considered minimal risk. The exercise test (6 minute walk) and training proposed in this study is considered no more than usual activity of daily living and is considered

moderate intensity exercise. There is a slight risk of abnormally high blood pressure, shortness of breath, muscle injury, and muscle soreness associated with exercise training in a sedentary (not used to exercise) population. There is a slight risk for pain and bruising with the venipuncture. There is a slight risk for loss of confidentiality (being identified) and there may be some discomfort felt by participants when answering questions about their medical history and during cognitive testing: The risks associated with the procedures of this study are minimal – no greater than those encountered during daily life. MRI scans: The MRI does not use x-ray radiation or radioactive material. The magnetism of the machine attracts certain metals, which could put participants at risk. Therefore, people with pacemakers, infusion pumps, metal prostheses, metallic-backed transdermal patches or metallic shrapnel will be excluded from the study. A checklist will be completed that addresses issues of MRI safety. Some people may feel somewhat closed-in (claustrophobic) during the MRI procedure. The MRI scans can get quite noisy and this may cause some discomfort. We will provide padding, a blanket, and ear plugs to ensure comfort. During the vascular testing; the blood pressure cuff could feel too tight and it may cause discomfort and there might be pressure on the neck from the ultrasound Doppler transducer, which could feel uncomfortable. Participants' can withdraw at any time and we will closely monitor them to ensure safety and comfort.

Anticipated Benefits: **This is a pilot study for feasibility** and no benefits should be expected. Walking exercise training has been associated with significant improvement in fitness (aerobic capacity), blood pressure, and ability to perform activities (physical function). The effect of exercise training on cognition is promising, but currently unknown.

Subject population: We anticipate randomizing 72 men and women with and without CKD between 60 and 80 years of age with no contraindications to moderate-intensity exercise that answered “yes” to the question “Do you feel like your memory or thinking skills have gotten worse recently?”. (please see detailed inclusion/exclusion criteria, section 4), In order to achieve this we anticipate sending 2000 letters to potential participants at UIC.

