3.0 Objectives/Aims

This is a pilot study for feasibility. The objective of this study is to test the hypothesis that older participants with moderate/severe chronic kidney disease (CKD) and preclinical cognitive impairment randomized to a 6-month home-based exercise program (n=12), will improve cognitive functioning and white matter integrity (WMI), compared to participants in a usual care control group (n=12). Our central working hypothesis is that the accelerated cognitive decline that occurs in CKD results, in part, from a vascular-dysfunction induced impairment of white matter integrity that is superimposed on a neurodegenerative process, and that exercise training may provide a cerebro-protective effect by improving systemic and cerebral vascular health.

Aim 1: Determine the feasibility and preliminary efficacy of a 6-month home-based exercise program to improve or maintain cognitive function in older participants with moderate/severe CKD and preclinical cognitive impairment, compared to usual care control group.

Hypotheses: Participants in the exercise group compared to the usual care control group at 6-months will:

- H1a. Demonstrate a higher score on composite global cognitive functioning.
- H1b. Demonstrate higher scores on executive functioning, learning/memory, and attention/information processing.

Aim 2. Determine the cerebro-protective effect of a 6-month exercise program compared to usual care on white matter integrity as quantified by Diffusion Tensor Imaging (DTI)-derived MRI measures of mean diffusivity (MD) and fractional anisotropy (FA). Intact white matter is important because it allows the brain to function properly and these are indices of white matter integrity.

- H2a. Participants in the exercise group will demonstrate an improvement in overall white matter integrity as measured by DTI, i.e., lower MD and higher FA, compared to control.

- H2b. Change in cognitive function will be positively correlated with change in WMI.

Aim 3 (secondary MRI outcomes): Determine the cerebro-protective effect of a 6-month exercise program compared to control on hippocampal volume and cerebral blood flow.

Hypothesis: Participants in the exercise group will have a larger hippocampal volume and improved cerebral blood flow post 6-month intervention, compared to the control group.

Study Duration: 12 months. Study duration for enrolled participants is anticipated to be 27 weeks.

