4.0 Eligibility

The eligibility check lists are attached. The PI ([name]) will ensure that subjects meet eligibility requirements. An eligibility checklist will be completed prior to any study participation during the initial phone screen and during the initial visit following informed consent. Eligibility criteria will be continuously monitored by the PIs and document via an eligibility checklist at baseline and at the 24 week follow up.

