4.1 Inclusion Criteria (self-reported and ICD code)

- English speaking men and women
- 60-80 years of age,
- self-experienced persistent decline in cognitive capacity determined as self-reported cognitive complaint (i.e., answering “yes” to the question: “Do you feel like your memory or thinking skills have gotten worse recently?” (before any clinical impairment of cognition has occurred);^{26,29,30}
- no history of major head trauma.

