3. c. Following these procedures participants will be asked to complete several questionnaires to assess their cognitive function. These questionnaires will be performed pre- and post-intervention with alternative forms where available to avoid practice effects. In addition to an overall global composite of cognitive functioning, we will evaluate the following domains of functioning with the below noted tests. (time~1 hour): The forms are titled: Learning & Memory=California Verbal Learning Test-II (CVLT-II); Attention/Information Processing=Trail Making Test Part A (TMT-A) and Digit Symbol Substitution Test (DSST); Executive Functioning, Phonemic and Semantic Fluency=Trail Making Test Part B and part M (TMT-B) and Digit Span subtest (DSp); Global Cognition=MOCA and WTAR (please see enclosed questionnaires). Quality of life will be assessed via the kidney disease quality of life questionnaire. These questionnaires will be administered at baseline and at 24 week follow up. The study satisfaction questionnaire will be administered at 24 weeks only.

Cognitive Outcomes (Table 1) will be performed pre- and post-intervention with alternative forms where available to avoid practice effects. In addition to an overall global composite of cognitive functioning, we will evaluate the following domains of functioning with the below noted tests. (time~1 hour)

Table 1. Cognitive Protocol

Domain	Tests	Outcome variables
Learning & Memory	California Verbal Learning Test-II (CVLT-II)	CVLT-II: Trials1-5 and learning slope; Long Delay Free Recall and Recognition Memory Discriminability
Attention/Information Processing	Trail Making Test Part A (TMT-A); Digit Symbol Substitution Test (DSST)	TMT-A time to completion and errors; DSST time to completion and errors
Executive Functioning	Phonemic and Semantic Fluency; Trail Making Test	Total correct words produced for Phonemic and Semantic fluency

	Part B (TMT-B); Digit Span subtest (DSp)	separately; TMT-B time to completion and errors; DSp total score
Global Cognition	MOCA and WTAR*	Total MOCA score; WTAR Estimated verbal IQ

*WTAR will only be given once as premorbid IQ is not anticipated to change with intervention

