3. d. Following these procedures a CCTS travel nurse will perform a standard venipuncture. Ten milliliters will be collected for determination of complete blood cell count and basic metabolic panel in order to characterize the sample. Coded blood samples will be analyzed by Quest diagnostics. An additional 10 ml will be collected for analysis of vascular health biomarker in [name] lab.

3. e. Following blood draw we will ask the participants to perform the short physical performance battery; participants attempt to stand for 10 seconds with their feet side by side, standing with the side of the heel of one foot touching the big toe of the other foot for about 10 seconds; and with the heel of one foot in front of and touching the toes of the other foot for about 10 seconds, they will then walk at a normal speed for a total of 4 meters (this test is repeated twice); the last part is called a chair rise where participants stand up from a chair 5 times (see manual in the appendix). Thereafter a 6-minute walk will be performed to determine total walking distance. Participants will follow standard testing procedures for older patients. Participants will be asked to walk up and down a 100 foot long corridor as fast as they can without running. They will turn around a cone placed at each end of the walk. No encouragement will be given and participants will be allowed to stop and rest whenever they need. Heart rate (measured by a polar heart rate monitor) will be monitored at rest, during and following the walking test to ensure safety. Blood pressure will be assessed prior to and immediately following the 6-minute walk. The 6-minute walk is considered to be within usual activities of daily living and should not pose any risk to participants. The 6-minute walk test is an accepted method for determination of total walking distance in older adults with chronic illness (see appendix for manual). The document used are titled “6 minute walk test” and Short Physical Performance Battery”. These will be administered at baseline and at the 24 week follow up.

The total time estimated for visit 1 is 2-3 hours.

Following completion of the initial visit we will ask the participants to wear a physical activity monitor, similar to a fancy pedometer, (actigraph GXT3 the size

of a small matchbox) on their hip for one week in order to collect their usual activities of daily living.

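### The aims concern moderate/severe CKD with 12 per arm, but the plan randomises 72 people with and without CKD and names no CKD analysis set

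*Combined protocol and SAP*

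**What the plan says.** **Population and number in the aims.** Section 3.0 tests its hypothesis in "older participants with moderate/severe chronic kidney disease (CKD) and preclinical cognitive impairment randomized to a 6-month home-based exercise program (n=12"), against a usual care group also of 12. Aim 1, which carries feasibility and preliminary efficacy, names moderate/severe CKD again. Aims 2 and 3 do not repeat it but sit under the same objective. Section 1.0 states the hypothesis for "older patients with moderate/severe CKD and pre-clinical cognitive impairment randomized to a 6-month home-based exercise program will improve cognitive function".

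**Population and number in the summary.** The subject population paragraph of Section 1.0 says "We anticipate randomizing 72 men and women with and without CKD between 60 and 80 years of age".

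**Who may enter.** Section 4.1 opens with "English speaking men and women" and goes on to age, a self-reported cognitive complaint and no major head trauma. It lists no CKD or eGFR requirement. Section 4.0 adds "The eligibility check lists are attached", but these are not in the text available. Section 5.0 recruits from records of patients with CKD, and also through media, general letters to people over 60, a research matching service and clinics. Section 6.0 gives ten participants with eGFR above 60 baseline testing only, then says that participants with eGFR above 60 will be asked whether they prefer baseline only or the intervention.

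**What is analysed.** Sections 9.0 and 12.0 describe feasibility statistics and a mixed model labelled intention to treat. Neither names a CKD set, subgroup, covariate or interaction. The adherence formula in Section 6.0 covers the exercise arm as a whole.

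**The concern.** The plan gives two different numbers randomised and two different populations, and the analysis sections do not choose between them. The pilot exists to supply feasibility rates and effect sizes for a larger trial of the Section 3.0 hypotheses. If people without CKD are randomised and pooled, those outputs describe a mixture whose make-up is not planned, while the aims are about CKD.

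Section 2.0 gives a reason not to assume that the two groups respond alike: it reports exercise as associated with better cognition in people without CKD and calls the effect in CKD unknown. If the CKD set is defined only after outcomes are available, the choice of set is open to influence from the results.

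**Working it through.** **1. Can the two counts be reconciled?** The inputs are 72 (Section 1.0) and 12 and 12 (Section 3.0).

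- 12 + 12 = 24, and 72 / 24 = 3.
- The plan has no power calculation or dropout allowance that might link them. Trying one anyway, 24 / (1 − d) for assumed dropout d of 10% to 40% gives 27 to 40. Reaching 72 would need d = 1 − 24/72 = 66.7%.

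The text offers no route from 24 to 72, so both cannot be the total randomised.

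**2. Can people outside the aims' population be randomised?**

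| Place | What it implies |
|---|---|
| Section 1.0, subject population | People without CKD are randomised |
| Section 4.1 | No listed criterion keeps them out |
| Section 6.0, control group text | eGFR above 60 may choose the intervention |
| Section 3.0, objective and Aim 1 | Moderate/severe CKD only |

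The first three agree with each other and differ from the fourth. A CKD criterion in the unseen checklists would move the conflict to Sections 1.0 and 6.0, not remove it.

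**3. Who is in the analysis?** The intention-to-treat wording says that participants with a missing observation are kept. It places no limit by CKD status, so it takes in all those randomised. That wording belongs to a model described for the full trial, but the same paragraph intends it to be run on the pilot data. For the descriptive rates no set is named.

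**4. What could pooling do to the effect?** Let q be the share without CKD and r the ratio of their effect to the CKD effect. The pooled effect is (1 − q) + q × r times the CKD effect. The plan gives neither q nor r, so these values are assumptions:

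- q = 0.25: r = 0 gives 0.75, r = 1 gives 1.00, r = 1.5 gives 1.125.
- q = 0.50: r = 0 gives 0.50, r = 1 gives 1.00, r = 1.5 gives 1.25.

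The shift can go either way and vanishes at r = 1 or q = 0. For an assumed CKD effect of 0.4 SD, the largest shift over these values is 0.4 × 0.25 = 0.10 SD or 0.4 × 0.50 = 0.20 SD.

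**5. What does a CKD-only set cost in precision?** The approximate 95% half-width for a difference between arms, in SD units and before dropout, is t × √(2/n), where n is the number per arm and t has 2n − 2 degrees of freedom.

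| n per arm | t | Half-width (SD) |
|---|---|---|
| 36 (all 72) | 1.994 | 0.47 |
| 27 (assumed) | 2.007 | 0.55 |
| 18 (assumed) | 2.032 | 0.68 |
| 12 (Section 3.0) | 2.074 | 0.85 |

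The shifts in step 4 are all below the pooled half-width of 0.47 SD.

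**The case against.** The strongest reply is that this is a descriptive pilot without a power calculation, so little turns on the set. Randomisation protects the comparison between arms whoever is enrolled. Section 6.0 draws a "complete blood cell count and basic metabolic panel in order to characterize the sample", so composition would ordinarily be reported and a CKD-only contrast can be recovered. Sections 9.0 and 12.0 refer back to the hypotheses of Section 3.0, so the target population is implied. The passage on eGFR above 60 may simply mean ten baseline-only places filled by preference. Broadening the aims to match Section 1.0 would also restore consistency.

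Most of this stands, and it limits the point. It does not answer it: an implied population is not a defined analysis set, two numbers randomised remain, and recoverable is not the same as prespecified. Broadening the aims would change the question of a study whose rationale and hypotheses are about CKD.

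Three stronger readings are tempting, and the documents do not support them.

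- A reader might combine the two counts and infer that 24 of the 72 have CKD. No passage says so; the 12 per arm may be a count that was not updated.
- A reader might divide each count by the planned mailing and infer a threefold difference in recruitment yield. Section 1.0 ties the mailing to the 72 only ("In order to achieve this we anticipate sending 2000 letters to potential participants at UIC"), other recruitment routes exist, and two targets divided by a planned mailing are not an observed result.
- A reader might count the ten baseline-only participants towards the gap. They are never randomised, so they cannot bear on it.

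Nor are the CKD-themed handouts or "Quality of life will be assessed via the kidney disease quality of life questionnaire" separate defects. They show intended emphasis.

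**Conclusion.** The point holds as a fault in defining the number randomised, the target population and the analysis set. As written, the plan states 24 and 72 as the number randomised, admits people outside the population of its objective and Aim 1, and would pool them. The effect sizes and the adherence and retention rates carried into the full trial would then describe a mixed population.

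A reader might go further and conclude that the pooled effect is diluted or biased. The documents do not support that. The CKD share of the 72 is unstated, the relative effect is unknown, and the direction could be either. The comparison between arms is valid for whoever is randomised. Recovering CKD status assumes that the visit 1 panel yields an eGFR, which Section 6.0 itself presupposes by sorting participants on eGFR.

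The fault should be fixed, because these outputs are the product of the pilot and the correction is a matter of text.

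**What to change.** 1. Reconcile Sections 1.0, 3.0, 4.1 and 6.0 to one number randomised, and state how many of those are planned to have moderate/severe CKD. Make clear that the ten baseline-only participants are outside that number, and whether their places are filled by preference.
2. Before outcome data are seen, define the CKD analysis set from the visit 1 eGFR, including what applies when a diagnosis code and the eGFR disagree.
3. Answer the objective and Aim 1, Aims 2 and 3 under the same objective, and the adherence and retention rates in that set. Report the other randomised participants and the pooled result separately.
4. Report recruitment as the number randomised by CKD status and by route. Give a CKD-specific yield only for the mailing to patients identified as having CKD in the medical records; the other routes have no clear CKD denominator, because the study's own blood is drawn only after consent.

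This takes protocol wording and one analysis-set definition. It needs no new test and excludes nobody. The real cost is a wider interval for the main set: 0.47 SD at 36 per arm, rising to as much as 0.85 SD if only 12 per arm have CKD. That last figure is the precision that the sample size in Section 3.0 already implies.

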2.0 Background/Scientific Rationale

Patients with CKD have more than a two-fold increased risk of cognitive impairment than those without CKD.¹⁻³ As many as 20-50% of patients with moderate CKD have established cognitive impairment or overt dementia.¹⁻⁷ Cognitive impairment leads to decreased medical care compliance, functional decline and loss of independence.⁸ There are no recommended treatments to prevent cognitive decline in CKD patients. There is therefore a need for therapies aimed to improve cognitive outcomes in older patients with CKD. The accelerated cognitive decline in older CKD patients is due, in part, to the CKD disease process itself, which creates a toxic vascular milieu that consists of chronic inflammation, oxidative stress, uremia, and systemic vascular endothelial dysfunction. This toxic internal vascular milieu leads to vascular dysfunction related impairment of the white matter that is superimposed on neurodegenerative damage.⁹ The white matter is important for coordinating interactions between different regions of the brain and is essential for normal functioning of the brain.¹⁰⁻¹⁴ Impaired white matter integrity appears to be a primary contributor to cognitive decline in CKD and is strongly affected by the internal vascular milieu.^{10,11} We have previously demonstrated that exercise training improves the vascular milieu in patients with CKD by reducing systemic inflammation and oxidative stress, and improving vascular function.^{15,16} Regular exercise and higher fitness levels in non-CKD patients with and without cognitive impairment has been associated with improved cognitive function, white matter integrity, and hippocampal volume suggesting a possible cerebro-protective effect of exercise.¹⁷⁻²⁸ This is conjectured to be due to an improvement in vascular function related increases in cerebral blood flow.¹⁸ The effect of exercise training on cognitive function and white matter integrity in CKD patients is unknown.

